7.4.3 Total daily opioid consumption (in oral morphine equivalents)

The amount of opioids taken as rescue will be calculated using the rescue medication page of the eCRF. If additional opioids, other than the study rescue medications, appear on the concomitant medications page and can be identified, those opioids will also be included (in terms of morphine equivalents) in the total consumed. For summaries of opioid consumption, the rescue medications for subjects who are discontinued from the efficacy portion of the study will be counted two ways. First, all medications on days up to and including the date of the discontinuation from efficacy will be included, but medications that were continued after the date of discontinuation from efficacy will not be counted. In a second analysis, all the medication for these subjects will be counted, regardless of whether it was taken before or after the subject discontinued from the efficacy portion.

Table 7-1 will be used to calculate the morphine milligram equivalents (MEQ) for each medication. The total opioid consumption for each day for each subject will be calculated as the sum of the MEQs of all of the medications taken on that day. For example, if a subject takes 5 MEQ morphine on Day 1 and Day 2, and 10 MEQ of Oxycodone on Day 2, the total consumption for Day 1 is 5 MEQ, and the total consumption for Day 2 is 15 MEQ. Subjects that take no opioids on a day will have a total opioid consumption value of zero for that day.

Table 7-1 Table of Morphine Milligram Equivalents

(from cdc.gov/drugoverdose/pdf)

| Opioid (Doses in mg/day) | Conversion Factor |
|----------------------------------|-------------------|
| Codeine | 0.15 |
| Fentanyl transdermal (in mcg/hr) | 2.4 |
| Hydrocodone | 1 |
| Hydromorphone | 4 |
| Morphine | 1 |
| Oxycodone | 1.5 |
| Oxymorphone | 3 |

Total opioid consumption will be calculated overall and for the same periods as the NPRS AUC values: 0-12 hours, 12-24 hours, 24-48 hours, 24-72 hours and 24-96 hours in addition, the periods 24h to Week 1 and 24h to Week 2 will also be summarized. An ANOVA with treatment arm as the main effect will be performed and the same types of comparisons as described in Section 7.4.1 will be presented. A separate summary containing only subjects that have taken at least one dose of rescue will be performed if warranted.

7.4.4 *Proportion of patients who drop out of the study due to inadequate analgesia from Day 1 to 15.*

Proportion of subjects who drop out of the study due to inadequate analgesia from Day 1 to 15 will be analyzed using Fisher's exact tests. Inadequate analgesia will be assumed if a subject drops out of the efficacy portion of the study due to inadequate analgesia, or if a subject drops out of the study entirely due to lack of efficacy or for an AE that is pain related. The reasons for discontinuation as documented on the eCRF end of study page will be used to determine the subjects who drop out of the study for inadequate analgesia.

A summary table will present the active vs. placebo group proportions, 95% confidence intervals and two-sided Fisher's exact p-values for the difference in proportions between each active group and placebo.

7.4.5 *Brief Pain Inventory-short form (BPI-SF)*

Individual questions will be listed.

In addition, two sub scores of the BPI will be calculated as follows:

Pain Severity Score = Mean of items 3-6

Pain Interference Score = Mean of items 9A-9G calculated only if more than 50%, or four of seven, of the total items have been completed on a given administration.

Questions 3-6, the Pain Severity Score and the Pain Interference Score will be analyzed using ANOVA with treatment as the main effect similar to previous analyses. The analysis results will be presented in a summary table with active vs. placebo difference means, standard errors, confidence intervals and p-values.

7.4.6 *PGE and IGE*

The proportions of subjects in each individual PGE and IGE category will be summarized by treatment group and time point and analyzed using the Cochran-Mantel-Haenszel mean score test (using equally spaced scores) at each time point to compare treatments across the 4 levels of outcomes (poor, fair, good, or excellent). In addition, Fisher's exact test will be performed to compare treatments across 2 levels of outcomes (Poor/Fair versus Good/excellent). The continuous PGE and IGE scores will also be analyzed using ANOVA with treatment as a main effect similar to presented previously. Individual PGE and IGE scores will be listed.

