7.1.2.2. Surgery

Subjects will then undergo primary, unilateral, transpositional first metatarsal osteotomy for correction of hallux valgus deformity. The bunionectomy surgery will be performed under light to moderate sedation which include propofol, fentanyl and/or midazolam. Subjects will receive regional anesthesia (MAYO Block) utilizing 0.5% bupivacaine (up to 30 cc total). The MAYO block should be done proximal to the surgical wound and should not involve the immediate area of the planned surgical incision. Upon completion of surgery, subjects will be observed for 48-hours in the clinic. AEs will be assessed during the surgery.

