9.1.3. Rescue Medications

While in-clinic, subjects will be treated with the prescribed analgesic regimen (oxycodone 5 mg every 2 hours); however, if subjects do not get adequate analgesic relief they will be discontinued from the efficacy portion of the study. At this point, subject's will receive standard of care analgesics (which may or may not include intravenous opioids). Regardless of discontinuation status, subjects will be followed for safety. Discontinuation affects the computation of the analgesic endpoint only. In previous post-operative Day 1 bunionectomy studies, oxycodone 5 mg every 2 hours has provided adequate analgesic relief to >90% of placebo subjects.

Day 1: Hours 0-24

- If needed for management of NPRS score of 4 or higher, oxycodone 5 mg every 2 hours.
- An NPRS should be completed within 15 minutes prior to use of rescue medication.

Day 2: Hours 25-48

- If needed for management of NPRS score of 4 or higher, oxycodone 5 mg every 2 hours.
- Subjects should complete their NPRS within 15 minutes prior to taking rescue medication.

Day 3 - Day 15:

- Over-the-counter standard of care analgesics may be used for management of pain.
- If needed for management of NPRS score of 4 or higher, oxycodone 5 - 15 mg every 4 - 6 hours.
- Subjects should complete their NPRS within 15 minutes prior to taking rescue medication.

Day 15 (post-visit) - Day 29/ET

- Over-the-counter standard of care analgesics may be used for management of pain.

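### SAP 7.4.3 reports opioid use in oral morphine equivalents but has no factor for intravenous opioids, and its by-day totals do not exclude operative fentanyl

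*SAP*

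**What the plan says.** **Scale and conversion.** SAP 7.4.3 is headed "Total daily opioid consumption (in oral morphine equivalents"), so the target scale is oral. It then states: "Table 7-1 will be used to calculate the morphine milligram equivalents (MEQ) for each medication". Table 7-1 has seven rows and no route column. Morphine has factor 1, hydromorphone 4 and oxycodone 1.5. The only fentanyl row is "Fentanyl transdermal (in mcg/hr"), with factor 2.4.

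**What is counted.** The rescue medication page is the main source. In addition: "If additional opioids, other than the study rescue medications, appear on the concomitant medications page and can be identified", then "those opioids will also be included (in terms of morphine equivalents) in the total consumed". Subjects discontinued from the efficacy portion are counted two ways: with medication through the date of that discontinuation, and with all medication.

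**Intravenous opioids.** Under Protocol 9.1.3, subjects without adequate relief on oxycodone move to "standard of care analgesics (which may or may not include intravenous opioids"). SAP 2.2 repeats this.

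**Operative opioids.** Protocol 7.1.2.2 describes surgery under "light to moderate sedation which include propofol, fentanyl and/or midazolam".

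**Start of counting.** SAP section 3 sets T0 at the end of dosing, and the period totals in 7.4.3 run in hours from 0. Protocol 10.4.5 starts the recording of rescue at the end of surgery. The by-study-day totals (Tables 14.2.3.1.1 and 14.2.3.1.2) add up everything taken on a day and state no starting time within Day 1.

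**The concern.** The table does not cover drugs and routes that the plan itself expects. A programmer who follows 7.4.3 literally would give an intravenous milligram of morphine or hydromorphone the same weight as an oral one, and would find no factor for intravenous fentanyl. Nothing says what to do with an opioid, route or unit that is not listed.

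The error need not be spread evenly over the arms. Intravenous opioids go to subjects whose analgesia failed, so any undercount sits where failures occur. Opioid consumption is a secondary endpoint in the protocol synopsis, and reduced opioid need is part of the product rationale in Protocol 5.1. The means are compared with placebo by ANOVA in groups of six, where one subject's value carries weight.

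Operative fentanyl is a different matter. Given before dosing, it cannot reflect the study drug and would only add noise to the Day 1 total.

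**Working it through.** **1. The plan's own example.** SAP 7.4.3 gives 5 MEQ on Day 1, and 5 MEQ plus 10 MEQ on Day 2. The sums are 5 and 5 + 10 = 15 MEQ, as stated. The example starts from values already in MEQ, so it tests neither the factors nor the route.

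**2. Do the intravenous doses enter the totals?** SAP section 3 takes the start of standard-of-care rescue as the date and time of discontinuation from efficacy. The first counting method includes that whole date, so the first intravenous dose is counted. The second method counts all such doses. Both are affected.

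**3. Yardstick.** One in-clinic rescue dose is 5 mg × 1.5 = 7.5 MEQ. At one dose every 2 hours, the most in 24 hours is 12 × 7.5 = 90 MEQ.

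**4. Size for one subject.** Two assumptions are not in the documents: a 10 mg intravenous morphine dose and an oral-to-intravenous potency ratio r of 2 to 3.
- As written: 10 × 1 = 10 MEQ.
- Oral equivalent: 10 × r = 20 to 30 MEQ.
- Shortfall: 10 × (r − 1) = 10 to 20 MEQ.

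**5. Effect on group means,** in the day or window that contains the dose:
- Dose cohort of 6: 10/6 = 1.7 to 20/6 = 3.3 MEQ.
- Pooled placebo, 5 cohorts × 2 = 10: 10/10 = 1.0 to 20/10 = 2.0 MEQ.

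A failure on placebo lowers the placebo mean and so understates any opioid-sparing effect. A failure in an active cohort does the opposite.

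**6. How often?** Protocol 9.1.3 says that the oxycodone regimen sufficed for more than 90% of placebo subjects in earlier studies, which implies a failure rate below 10%. The chance of at least one failure among 10 placebo subjects is 1 − (1 − p)^10:

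| Failure rate p | Expected failures (10p) | Chance of at least one |
|---|---|---|
| 10% | 1.0 | 65% |
| 5% | 0.5 | 40% |
| 2% | 0.2 | 18% |

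Not every failure would receive an intravenous opioid, so these are upper figures for the event that matters.

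**7. Operative fentanyl.** Set the sections side by side:
- SAP 5.3 classes a drug stopped before dosing begins as prior and a later stop as concomitant. SAP 7.4.3, however, refers to what appears on a CRF page, not to that class.
- Protocol 7.1.4 places dosing before skin closure, so T0 falls before the end of surgery.
- Fentanyl given before T0 lies outside every hour window. It can still enter the Day 1 by-day total and the overall total if it is on the concomitant medications page.
- Fentanyl given between T0 and skin closure could also enter the 0–12 h total.

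**The case against.** **A reader might infer that opioid counting has no start time at all.** The documents do not support that. T0 is defined, the hour windows start at 0, and rescue recording starts at the end of surgery. Only the by-day and overall totals, and the short interval between T0 and skin closure, are left open.

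**A reader might also multiply operative fentanyl by 2.4.** An assumed 50 to 100 mcg would give 120 to 240 MEQ, more than the 90 MEQ daily maximum from step 3. But that factor is labelled for a transdermal rate in mcg/hr. Followed as labelled, the table gives intravenous fentanyl no factor, so these figures describe misuse of the table and not the plan. No fentanyl dose is stated in either document.

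**Nor can one conclude that opioid use will be mis-stated.** Intravenous opioids and fentanyl are both optional, few failures are expected, and the potency ratio is an outside assumption. The CRF is not supplied. Sedation drugs may be recorded with the surgery details, which SAP 8.10 lists separately.

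**The consequence is limited.** SAP 7.3 and 7.4 treat the endpoint as exploratory with nominal p-values. Dropout for inadequate analgesia, time to first rescue and the proportion using rescue capture failures without any conversion factor. Medications are also listed by subject.

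All of this stands and limits the weight of the point. It does not answer the central gap: the stated rule gives a wrong value for a treatment that both documents foresee.

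**Conclusion.** The point holds in a conditional form. If intravenous opioids are used after failure of the oxycodone regimen, Table 7-1 converts morphine and hydromorphone as if oral and offers nothing valid for fentanyl, in both counting methods. Under the dose and potency assumptions in step 4, one such subject is undercounted by 10 to 20 MEQ, with the mean shifts given in step 5. The error depends on arm only if failures do. If they are commoner on placebo, any opioid-sparing effect is understated.

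The operative-fentanyl gap is narrower. It concerns the by-day and overall totals and the interval from T0 to skin closure, and it depends on where the CRF records sedation. Its size cannot be derived from the documents. Both gaps are worth closing before database lock, but neither bears on the primary safety and pharmacokinetic objectives.

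**What to change.** In SAP 7.4.3:
1. Add route-specific rows to Table 7-1 for intravenous morphine, intravenous hydromorphone and intravenous fentanyl (per mcg), all as oral equivalents with the source cited. State that the transdermal factor applies to patches only.
2. Add a rule for any opioid, route or unit not in the table: who assigns the factor, before unblinding, and how the case is flagged.
3. Exclude opioids given for operative sedation from all totals, including those given between T0 and skin closure.
4. Start the Day 1 and overall totals at T0, as the hour windows already do.

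The cost is a table edit and a few sentences before database lock. It relies on route and time being recorded for each opioid, which should be checked against the CRF.

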Secondary (efficacy):	
 1. Area-under-the-curve (AUC) over various time points using NPRS score (0–10), with adjustment for use of analgesic therapy/medication. 2. Mean average daily NPRS score of 2 daily diary assessments. 3. Mean daily opioid consumption (in morphine equivalents). 4. Proportion of patients who drop out of the study due to inadequate analgesia from Day 1 to 15. 5. Brief Pain Inventory-short form (BPI-SF) scores at the Day 8 (Week 1), Day 15 (Week 2) and Day 29 (Week 4) or ET clinic visits. 6. Patient Global Evaluation (PGE) at the Day 8 (Week 1), Day 15 (Week 2) and Day 29 (Week 4) clinic visits. 7. Investigator Global Evaluation (IGE) at the Day 8 (Week 1), Day 15 (Week 2) and Day 29 (Week 4) clinic visits.
Eligibility: Inclusion Criteria:	
 1. Male or female aged 18 - 65 years old, inclusive. 2. Planning to undergo a primary unilateral first metatarsal bunionectomy repair, without collateral procedures. 3. Be American Society of Anesthesiology (ASA) physical Class 1 or 2. Appendix J 4. In good health and capable of undergoing a bunionectomy under regional anesthesia. 5. No additional planned surgeries other than a bunionectomy during the

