7.3 Exploratory Efficacy Endpoints

- Area under the curve (AUC) of subject's NPRS will be examined over various time periods, including but not limited to: AUC(0-12), AUC(12-24), AUC(24-48), AUC(24-72), AUC(24-96), AUC(24h to Week 1), and AUC(24h to Week 2).
- Mean daily opioid consumption (in morphine equivalents) over the same time periods as the AUC calculations above.
- Proportion of patients who drop out of the study due to inadequate analgesia from Day 1 to 15.
- Brief Pain Inventory-short form (BPI-SF) scores at the Day 8 (Week 1), Day 15 (Week 2) and Day 29 (Week 4) or ET clinic visits.
- Patient Global Evaluation (PGE) at the Day 8 (Week 1), Day 15 (Week 2) and Day 29 (Week 4) clinic visits.

- Investigator Global Evaluation (IGE) at the Day 8 (Week 1), Day 15 (Week 2) and Day 29 (Week 4) clinic visits.
- Time to first use of rescue medication.
- Percent of days that rescue medication was used.

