14 APPENDICES

14.1 Tables, Figures and Listings for Final Study Report

14.1.1 Tables

| | | |
|------------------|---|--|
| Table 14.1.1 | All Subjects | Summary of Subject Disposition |
| Table 14.1.2 | All Randomized Population | Summary of Protocol Deviations |
| Table 14.1.3 | All Randomized Population | Summary of Demographic and Baseline Characteristics |
| Table 14.1.4 | Safety Population | Summary of Concomitant Medications by ATC Class and Preferred Term |
| Table 14.1.5 | Safety Population | Summary of Subject NPRS and NPRS at Rescue Diary Compliance |
| Table 14.2.1.1 | Safety Population | ANOVA Analysis of AUC of NPRS - WOCF |
| Table 14.2.1.2 | Safety Population | ANOVA Analysis of AUC of NPRS - LOCF |
| Table 14.2.2.1 | Safety Population | ANOVA Analysis Mean Average Daily NPRS of 2 Daily Diary Assessments |
| | | |
| Table 14.2.3.1.1 | Safety Population | Summary of Daily Opioid Consumption (in Morphine equivalents) by Study Day |
| Table 14.2.3.1.2 | Safety Population | Summary of Daily Opioid Consumption (in Morphine equivalents) by Study Day up to Discontinuation of Efficacy Portion |
| Table 14.2.3.2.1 | Safety Population | ANOVA Analysis Mean Daily Opioid Consumption (in Morphine Equivalents) |
| Table 14.2.3.2.2 | Safety Population | ANOVA Analysis Mean Daily Opioid Consumption (in Morphine Equivalents) up to Discontinuation of Efficacy Portion |
| Table 14.2.3.3 | Safety Population – Subjects Who Took Any Opioid Medication | ANOVA Analysis Mean Daily Opioid Consumption (in Morphine Equivalents) |
| Table 14.2.4 | Safety Population | Fishers Analysis of Proportion of Drop Out Due to Inadequate Analgesia |
| Table 14.2.5 | Safety Population | ANOVA Analysis Brief Pain Inventory (BPI-SF) Pain and Interference Subscales |

| | | |
|------------------|-------------------|---|
| Table 14.2.6 | Safety Population | CMH and Fishers Analysis of Patient Global Evaluation (PGE) |
| Table 14.2.7 | Safety Population | CMH and Fishers Analysis of Investigator Global Evaluation (IGE) |
| Table 14.2.8.1.1 | Safety Population | Fishers Analysis of Percent of Subjects using Rescue Medication Over Time |
| Table 14.2.8.1.2 | Safety Population | Fishers Analysis of Percent of Subjects using Rescue Medication Over Time up to Discontinuation of Efficacy Portion |
| Table 14.2.8.2.1 | Safety Population | Summary of Percent of Subjects Using Rescue Medication by Day |

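### The opioid endpoint is named as mean daily consumption, but SAP 7.4.3 derives only undivided totals with no denominator, so early stoppers can score as lower opioid users

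*SAP*

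**What the plan says.** Protocol synopsis (secondary efficacy endpoints) and Protocol 10.6.3 list mean daily opioid consumption in morphine equivalents. SAP 7.3 repeats it as "Mean daily opioid consumption (in morphine equivalents) over the same time periods as the AUC calculations above". The ANOVA tables in SAP 14.1.1 (14.2.3.2.1, 14.2.3.2.2 and 14.2.3.3) carry the same name, for example "ANOVA Analysis Mean Daily Opioid Consumption (in Morphine Equivalents) up to Discontinuation of Efficacy Portion".

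SAP 7.4.3 works differently. It defines a total for each day and then states "Total opioid consumption will be calculated overall and for the same periods as the NPRS AUC values", naming 0-12, 12-24, 24-48, 24-72 and 24-96 hours, 24 h to Week 1 and 24 h to Week 2. The next sentence begins "An ANOVA with treatment arm as the main effect will be performed and the same types of comparisons as described in Section 7.4.1 will be". No daily mean and no divisor is defined.

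Subjects discontinued from the efficacy portion are counted in two ways. In the first, "medications that were continued after the date of discontinuation from efficacy will not be counted". In the second, "all the medication for these subjects will be counted, regardless of whether it was taken before or after the subject discontinued" from efficacy. A day on which no opioid is taken scores zero. Nothing is said about days on which the subject is no longer observed. The drop-out imputation in SAP 7.1 covers pain scores only.

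**The concern.** The variable in the table titles is not the variable derived in the text, so two programmers could fill the same table with different numbers. The choice also affects interpretation. A sum grows with the time over which it is counted. If counting stops early and the missing days contribute nothing, the subject's total is low whatever the rate of use was.

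The subjects most exposed are those who stop for inadequate analgesia. SAP 7.1 gives them their worst prior pain score, while the period total credits them with low opioid use, so the two outcomes move in opposite directions for the same event. With six subjects per dose and ten pooled placebo subjects, one or two such cases can shift a group mean. The direction depends on which arm stops more often. More stopping on placebo hides a true opioid-sparing effect, and more stopping on a CA-008 dose creates an apparent one.

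**Working it through.** **1. The SAP's own example.** SAP 7.4.3 gives 5 MEQ on Day 1 and 5 + 10 = 15 MEQ on Day 2, and this reproduces. Over the two days the total is 20 and the mean daily value is 20/2 = 10. The two definitions report different numbers.

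**2. Complete follow-up.** If every subject is counted for the same P days, total = P x daily mean, and an ANOVA is unaffected by a constant multiplier. A test draw of 10 against 6 subjects gave p = 0.081 for both versions. Here only the scale changes.

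**3. Unequal counted time.** Assume that 24 h to Week 2 is nominally Day 2 to Day 15, so 15 - 2 = 13 days. The rates below are illustrative; 30 MEQ/day is 30/1.5 = 20 mg oxycodone.

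| Subject | Days counted | Total | Total / days counted | Total / fixed 13 days |
|---|---|---|---|---|
| 30 MEQ/day, stops early | 1 | 30 | 30 | 2.31 |
| 10 MEQ/day, completes | 13 | 130 | 10 | 10 |

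The heavier user's total is 1 - 30/130 = 77% lower. Dividing by a fixed 13 days keeps the wrong order, so the denominator decides the matter and the word daily alone does not.

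**4. Group effect under flat use.** Assume equal true use of about 20 MEQ/day (SD 10) in both arms, and that a share q of placebo subjects is counted for 1 of 13 days. The expected spurious active-minus-placebo difference in totals is q x 20 x 12, which is 24, 48 and 72 MEQ for q = 10%, 20% and 30%. Simulation (20,000 runs, 10 placebo and 6 active) gave 24, 49 and 73, while the mean over counted days stayed near 0. With a true benefit (30 against 20 MEQ/day) and q = 30%, the expected totals are 30 x (0.7 x 13 + 0.3 x 1) = 282 on placebo and 20 x 13 = 260 on active. That is a difference of -22 (simulated -21) in place of -130. On prior studies, Protocol 9.1.3 expects adequate relief in more than 90% of placebo subjects on Day 1, so q = 10% is the scenario nearest to the documents.

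**5. One early stopper in a group of six.** The subject leaves on Day 6 and is counted for 6 - 2 = 4 days. The result depends on the shape of use.

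| Pattern (assumed) | Completer total; rate | Leaver total; rate | Shift in mean total | Shift in mean rate |
|---|---|---|---|---|
| Flat 30/day | 390; 30 | 120; 30 | (120 - 390)/6 = -45 (-11.5%) | 0 |
| 30/day for 4 days, then 5/day | 120 + 9 x 5 = 165; 12.7 | 120; 30 | (120 - 165)/6 = -7.5 (-4.5%) | (30 - 12.7)/6 = +2.9 (+23%) |

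Under falling use the total understates slightly and the rate over counted days overstates more.

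**6. Period ends.** If Week 2 ended at the actual Day 15 visit (+/-2 days), the period would run 11 to 15 days. At a flat 30 MEQ/day that is 330 to 450, a ratio of 1.36, or about +/-15% around 13 days. Under the falling pattern the totals are 155 and 175 (13% apart) and the rates 14.1 and 11.7 (21% apart). SAP 7.4.3 does not say whether the visit or a nominal time ends the period.

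**The case against.** The ANOVA sentence in SAP 7.4.3 names no dependent variable. The section title contains both total and daily, and the tables it feeds are titled mean daily, so averaging the day totals is a natural reading. A reader might infer that the sponsor will certainly analyse undivided sums. The documents do not establish that; they leave it open. The absence of any defined mean or denominator still stands.

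Much of the exposure is limited. Five of the seven named periods are fixed hour windows. In the in-clinic windows at most 12 or 24 hours of use can be lost. Under Protocol 9.1.3, subjects with inadequate in-clinic relief leave only the efficacy portion and are still followed, so the second count keeps their later opioids, and by-day summaries are also planned. In that count the remaining gap is full study withdrawal, where SAP 7.1 expects little missing data. No drop-out rate is given.

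A reader might also take the 36% and 12% figures as estimates of bias. They are illustrations. The first assumes visit-tied period ends and flat use, and nothing links visit timing to arm, so it would add noise and not bias. The second assumes flat use and one hypothetical leaver. Finally, dividing by counted days is not a cure in itself. The falling-use example shows an error in the other direction, and that criticism stands.

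**Conclusion.** The mismatch is real: the endpoint and table titles are a daily mean, and the derivation supplies only totals. Read as written, days after withdrawal, and days dropped after efficacy discontinuation in the first count, add nothing, so early stoppers, including treatment failures, score as lower users. The effect is largest in the up-to-discontinuation tables and in 24 h to Week 1, 24 h to Week 2 and overall. It is small in the in-clinic windows, and only a change of scale when follow-up is complete.

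Its size cannot be estimated from the documents. Under flat use with early stopping confined to placebo, it is about 24 MEQ in the 13-day total at 10% stopping. For a single Day 6 leaver in a dose group it ranges from -4.5% to -11.5% of the mean total across the two patterns tried. The endpoint is listed as exploratory, p-values are nominal (SAP 7.4), and the study is not designed to detect an analgesic difference (Protocol synopsis). The consequence is therefore for how the opioid results are read, and no confirmatory conclusion depends on it. It should be corrected before database lock.

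**What to change.** In SAP 7.4.3:

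- Make the ANOVA variable mean daily MEQ = MEQ counted in the period / days (hours/24) counted in that period, for every period and for overall.
- End Week 1, Week 2 and overall at fixed nominal times.
- State that days after study withdrawal, and days excluded after efficacy discontinuation in the first count, are not scored as zero and are not in the denominator. A subject with no counted time in a period has no value for it, and the number of such subjects should be shown.
- Keep the period total as a sensitivity analysis, with both versions reported side by side.
- Align the 7.4.3 title, the table titles and Listing 16.2.7.4, which at present refers to an AUC of total MEQ.

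The cost is SAP wording, one denominator in the program and one additional set of tables. No new data are needed, since SAP section 6 already derives days of outpatient participation for diary compliance. The downside is that postoperative opioid use is likely to fall over time, so the rate over counted days weights an early stopper's high-use days and can overstate that subject's consumption. This is the reason for showing both versions.
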